Co-Investigators	, [name] (Iron River Hospital, MI) [name] (Elkhart Hospital, IN)
Type of Study	Prospective, investigator initiated, multicenter, non-randomized single arm, open label.
Study Duration	6 Months for primary endpoint. 1 and 2 year follow-up for QOL per SOC.
Number of Patients Number of Sites	50 patients from 3 sites
Follow-Up Schedule	Following TIF procedure, patients will be expected to complete follow-up visits at the 2-Week, 3-Month, and 6-Month time points. Additional follow-up to be completed at 12 and 24 months to assess long-term symptom relief. Consideration will be given to extending follow-up with questionnaires to 3, 4 and 5 years. The study will be considered complete (with regard to the primary effectiveness endpoint) after all patients have completed the 6-Month follow-up visit.

Inclusion Criteria	
 1. Age 18-80 years 2. Dependent upon daily PPIs for > 6 months. Daily use is defined as a double dose, or full dose or half dose taken daily for more than 80% of the total number of days during the proceeding evaluation period 3. Troublesome symptoms, specifically heartburn or regurgitation, while on optimized dose of PPI's Troublesome heartburn or regurgitation symptoms are those which occur a minimum of 2 days a week and are mild to severe in severity 4. Abnormal ambulatory (Bravo) pH study after off PPI therapy for 7 days, i.e. > 5.3% of the time with pH < 4 in a 48-hour monitoring period 5. Normal or near normal esophageal motility (by Upper GI/ esophagram or manometry as required) 6. Pre-enrollment Hiatal Hernia (axial height and transverse dimension) from > 2 cm up to 4 cm inclusive. 7. Patient willing to cooperate with post-operative dietary recommendations and assessment tests at the requisite follow-up visits 8. Signed informed consent

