In this context, an ideal study would consist of enrolling patients who suffered from persistent troublesome symptoms while on optimized dose of PPIs. The prospective study is open-label, non-randomized, and investigator initiated at multiple (3) sites (n=50). The primary endpoint is a clinically significant pH improvement, i.e. normalization, at the 6 month post-op mark. The proportion of patients with normalized esophageal acid exposure after 6 months will be compared to that of the previous EsophyX RESPECT trial to demonstrate equivalent (non-inferior) effectiveness. A sequence of follow-up visits will be required (2 week, 3 month, 6 month) to monitor symptom presence and PPI intake via Quality of Life surveys in addition to the primary endpoint. This follow-up and symptom monitoring will include evaluation of potentially new onset symptoms such as dysphagia and gas bloating commonly associated with the NF procedure.

4. Study Objective

Evaluation of the relative merits, safety and effectiveness of the EsophyX Z transoral device in performing an advanced TIF procedure preceded by laparoscopic Hiatal Hernia repair (hiatal hernias >2cm and \leq 4 cm) in PPI- prescribed patients with “troublesome symptoms” per the Montreal consensus definition.

5. Study Hypotheses

5.1. *Primary Efficacy Hypothesis 1*

At 6-month follow-up, the proportion of TIF patients with normalized esophageal acid exposure will be statistically non-inferior to results from the EGS RESPECT study.

5.2. *Secondary Efficacy Hypothesis 1*

The proportion of TIF2 patients who are free of “troublesome” symptoms will be the same as or higher than the results from the EGS RESPECT study.

5.3. *Secondary Efficacy Hypothesis 2*

At 6-month follow-up, \geq 50% of the TIF patients will have a clinically significant reduction in PPI consumption as compared with their pre-TIF consumption

5.4. *Primary Safety Hypothesis 1*

At 6-month follow-up, no increase in medically significant adverse events as compared with the RESPECT study

5.5. *Secondary Safety Hypotheses 1*

[figure not shown]
At 6-month follow-up, no new onset symptoms and side effects frequently associated with Nissen fundoplication procedures including dysphagia and gas bloat.

6. Study Design**6.1. *Study Population***

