7.1. Selection Criteria

The table on the following pages outlines the specific inclusion and exclusion criteria for the study. Before randomization in the study, a patient must meet all of the inclusion and exclusion criteria.

Inclusion Criteria:	
1.	Age 18-80years
2.	Dependent upon daily PPIs for > 6 months. Daily use is defined as a double dose, or full dose or half dose taken daily for more than 80 % of the total number of days during the proceeding evaluation period
3.	Troublesome symptoms, specifically heartburn or regurgitation, while on optimized dose of PPI's. Troublesome heartburn or regurgitation symptoms are those which occur a minimum of 2 days a week and are mild to severe in severity.
4.	Abnormal ambulatory (Bravo) pH study after off PPI therapy for 7 days, i.e. >5.3% of the time with pH < 4 in a 48-hour monitoring period
5.	Normal or near normal esophageal motility (by Upper GI/ esophagram or manometry as required)
6.	Pre-enrollment Hiatal Hernia (axial height and transverse dimension) from > 2cm and up to 4 cm inclusive
7.	Patient willing to cooperate with post-procedure dietary recommendations and assessment tests at the requisite follow-up visits
8.	Signed informed consent
Pre-enrollment Exclusion Criteria:	
1.	BMI > 35
2.	Hiatal hernia \leq 2 and > 4 cm
3.	Esophagitis Los Angeles grade C or D
4.	Esophageal ulcer
5.	Esophageal stricture
6.	Long-segment Barretts esophagus (Prague: C > 1, M > 3)
7.	Esophageal motility disorder
8.	Pregnancy or plans for pregnancy in the next 12 months (in females)
9.	Immunosuppression
10.	ASA > 2
11.	Portal hypertension and/or varices
12.	History of previous resective gastric or esophageal surgery, cervical spine fusion, Zenker's diverticulum, esophageal epiphrenic diverticulum, achalasia, scleroderma or dermatomyositis, eosinophilic esophagitis, or cirrhosis
13.	Active gastro-duodenal ulcer disease
14.	Gastric outlet obstruction or stenosis
15.	Severe gastroparesis or delayed gastric emptying confirmed by solid-phase gastric emptying study if patient complains of postprandial satiety during assessment
16.	Coagulation disorders
17.	Symptoms including gas bloat and dysphagia.
18.	Any other presenting condition that in the opinion of the investigator would not make participation in this study in the patients best interest.
Post-enrollment Exclusion Criteria:	
1.	Inability to repair Hiatal hernia with at least 2cm of intra-abdominal esophagus length.

7.2. *Withdrawal*

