While study withdrawal is discouraged, patients may withdraw from the study at any time, with or without reason and without prejudice to further treatment. Withdrawn patients will not undergo any additional follow-up. In all cases of withdrawal, the reason(s) for withdrawal (if given) will be recorded upon study termination.

8. Study Methods and Techniques

8.1. *Clinical Symptom Assessments*

The following four GERD-specific questionnaires will be used to assess typical and atypical symptoms, their frequency and intensity, as well as their impact on daily life, relationships, quality of life, state of mind, worries and concerns, sleep and diet.

- Reflux Disease Questionnaire (RDQ)
- GERD HRQL Quality of life assessment
- GERD GSRS Quality of life assessment
- RSI Questionnaire for atypical symptoms

- The time needed for completion of all four questionnaires is estimated for 35 minutes maximum.
- A $\geq 50\%$ improvement in the total GERD-HRQL and GERD-GSRS scores compared to the baseline off PPIs will be considered clinically significant.
- A reduction in severity from \geq moderate to \leq mild and/or a reduction in frequency from ≥ 2 days per week to ≤ 1 day per week is indicative of a clinically significant result as measured by the Reflux Disease Questionnaire (RDQ).

8.2. *PPI Usage*

The use of PPIs plus other GERD medication such as histamine receptor antagonists (H2RA) and antacids will be recorded in a medication diary using generic names (**Table 3**) and classified according to the daily dose and frequency.^{18, 21}

Usage will be defined as “Daily” if a double dose, full dose or half dose is taken daily for more than 80% of the total number of days during the proceeding follow-up period.

Note: “Full Dose” is defined as the first number of mg listed for each PPI in the following table.

Table 3. Proton Pump Inhibitors (PPI)

Generic Name	Brand Names	Available Pill Sizes (mg)
Esomeprazole	Nexium	20, 40
Lansomeprazole	Prevacid, Dakar, Lando, Lanzor, Prezal, Lanzol	15, 30
Omeprazole	Prilosec, Losec, Logastric	10, 20, 40
Pantoprazole	Protonix, Zurcal, Pantozol, Zurcale	20, 40
Rabeprazole	Aciphex, Pariet	20

8.3. *Upper GI Endoscopy*

- Diagnosis of esophagitis according to the Los Angeles classification confirmed by esophageal biopsy.²²
- Hiatal hernia size will be diagnosed based on the distance from Z-line to diaphragmatic impression measured in cm at retraction of the endoscope without insufflation.

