The following pre-procedure data must be collected in order to determine eligibility:

- Informed consent signing
- Physical Examination
- Days since last PPI intake (prior to BRAVO pH study)
- EGD with optional biopsy
- High resolution motility studies (optional)
- Upper GI endoscopy
- Bravo pH studies (48 hours)

Patients who have met all entry criteria are enrolled to the study.

9.2. *Prior to the Study Procedure*

- The usage of any anticoagulants will be discontinued before TIF for at least 10 days.
- 12-hours before the procedure, the patient is expected to be fasting.
- Immediately before the procedure, each patient will undergo an endoscopic examination of the stomach and esophagus.

9.3. *During the Study Procedure*

A Transoral Incisionless Fundoplication will be performed following the standard laparoscopic Hiatal Hernia Repair and closure of the diaphragmatic defect (crura closure will be made

posterior with 2-3 separate stitches). The patient will be terminated from the study if hiatal hernia cannot be repaired, with at least 2 cm intra-abdominal esophageal length.

TIF Procedure (Treatment)

The TIF procedure (treatment) will be conducted under continuous visualization following a standard TIF2.0 protocol (**Figures 8**).

[figure not shown]

Figure 8. Standard TIF2 protocol

The usage of any anticoagulants will be discontinued before HHR and TIF 2.0 for at least 10 days. Patients are expected to fast for 12 hours before the procedure. Antibiotic prophylaxis will be administered during induction of general anesthesia (oro-tracheal intubation and anti-emetic protocol; dehydrobenzoperidol, dexamethasone, Zofran, Primperan).

As stated in Section 10.2, immediately before the procedure, each patient will undergo an endoscopic examination of the stomach and esophagus. The EsophyX ZR will be inserted transorally through a bite-block into the esophagus with the patient in either in supine, or 45 degrees or left lateral position.

During a single insertion of the device, a valve similar to that created through antireflux surgery will be reconstructed by retraction of full-thickness plications and tailored placement of multiple fasteners circumferentially 1-3 cm above the Z-line. The procedure is expected to last for 30-45 minutes. The quality of the

created valve will be evaluated by an endoscopic examination immediately after the procedure. Any complications related to the procedure will be recorded.

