Effectiveness Population - Per the Intent-to-Treat principle, all enrolled patients who receive the protocol TIF 2.0 procedure will be included in the effectiveness analysis.

Safety Population - Safety analysis will include all enrolled patients who receive any portion of the protocol required Hiatal Hernia Repair or TIF 2.0 procedures.

Missing data: All analyses will be based on available data. Missing data will not be imputed by methods.

10.2. *Statistical Analysis Plan*

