10.2.3 Safety Analysis

Treatment emergent adverse events, i.e. adverse events occurring during or after the first protocol procedure (i.e. hiatal hernia reduction), will be summarized. The proportion of patients with medically significant adverse events will be compared to the same proportions observed in the RESPECT study.

In addition, the number and proportion of subjects reporting any given adverse event, including any clinically significant hiatal hernia repair complications and new onset symptoms (dysphagia, gas bloat) should they occur, will be tabulated. Separate tables will be constructed for (a) all reported treatment emergent adverse events, (b) protocol procedures (hiatal hernia reduction, TIF) related adverse events, and (c) serious adverse events.

10.1. *Sample Size and Power Estimation*

For the primary endpoint, proportion of patients with normalized esophageal acid exposure at 6 months post TIF procedure, 44% was observed in the EGS RESPECT study. It is assumed that the true underlying rate for HEURISTIC treatment would be the same, i.e. 44%. In order to reject an inferior normalization rate of 24% at a 1-sided $p < 0.05$ level, the observed 6-month normalization rate in HEURISTIC must be 18/50 (36%) or higher. With 50 evaluable subjects, the chance (power) for successfully reaching this goal is 0.90.

11. Clinical Effectiveness Endpoints and Evaluation Criteria

11.1. *Clinical effectiveness*

Primary effectiveness endpoint and evaluation criterion

The primary efficacy endpoint is normalization in esophageal acid exposure at 6 months post TIF procedure. Normalization in esophageal acid exposure is defined as $\leq 5.3\%$ of time with $\text{pH} < 4$ in a 48-hour monitoring period.

Secondary effectiveness measures and evaluation criteria

Secondary effectiveness measures include free of “troublesome” heartburn and/or regurgitation symptoms and a clinically significant reduction in PPI use.

Per Montreal Consensus definition, troublesome symptoms are mild to severe symptoms which occur a minimum of 2 days a week.

A clinically significant PPI consumption reduction is defined as from daily use to occasional use or none at all. Daily use is defined as a double dose, or full dose or half dose taken daily for more than 80 % of the total number of days during the proceeding follow-up period.

Table 5. Study Effectiveness Endpoints and Success Criteria

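### The stated power of 0.90 needs all 50 planned patients to be evaluable, and the plan allows for none of the losses its own rules create

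*Combined protocol and SAP*

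**What the plan says.** - **Planned size.** The Protocol Synopsis gives "50 patients from 3 sites". Section 3 (Study Design Rationale) repeats it: "investigator initiated at multiple (3) sites (n=50". No other enrolment figure appears.
- **Power.** The second section numbered 10.1 (Sample Size and Power Estimation) assumes a true 6-month normalization rate of 44%, tests against 24% at one-sided p < 0.05, and sets the bar at 18 of 50. It concludes: "With 50 evaluable subjects, the chance (power) for successfully reaching this goal is 0.90". Section 10.2.2 gives the same test and the same bar, also for 50 evaluable patients.
- **Point of enrolment.** Section 9.1, Final Screening: "Patients who have met all entry criteria are enrolled to the study". This precedes both procedures.
- **Ways out after enrolment.** Section 7.1 lists as a post-enrolment exclusion "Inability to repair Hiatal hernia with at least 2cm of intra-abdominal esophagus length", and Section 9.3 adds: "The patient will be terminated from the study if hiatal hernia cannot be repaired". Section 7.2: "Withdrawn patients will not undergo any additional follow-up".
- **Who is analysed.** Under the first Section 10.1 (Analysis Populations and Missing Data Handling), "all enrolled patients who receive the protocol TIF 2.0 procedure will be included in the effectiveness analysis". The same section bases all analyses on available data, without imputation.

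**The concern.** The number planned and the number evaluable are both 50. They can be equal only if every enrolled patient has a successful repair, receives TIF, stays in the study, and completes the repeat 48-hour BRAVO test at 6 months after at least 7 days off antisecretory drugs. The plan's own rules anticipate failures at several of these steps, yet it contains no attrition allowance, enrolment inflation or replacement rule. The synopsis and Section 3 do not say whether 50 counts enrolled or evaluable patients.

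At stake is the chance of a false negative. Someone who reads the synopsis beside the sample-size section will take the risk of missing the goal, when the true rate is 44%, to be 10%. If 50 are enrolled and any are lost, it is higher.

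**Working it through.** **Inputs from the documents.** Null rate p0 = 44% − 20% = 24%; assumed true rate p1 = 44%; exact binomial test, one-sided p < 0.05 (Section 10.2.2 and the sample-size section). Planned size 50 (Synopsis, Section 3).

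**Input that is assumed.** The loss rate r, taken from 2% to 20%, with loss independent of the pH outcome. The documents give no rate.

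**Step 1: reproduce the plan's figure.** For X ~ Binomial(50, p):

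- P(X ≥ 17 | 0.24) = 0.0718, which is above 0.05
- P(X ≥ 18 | 0.24) = 0.0384, which is below 0.05, so 18/50 is the correct bar
- P(X ≥ 18 | 0.44) = 0.901

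The stated 0.90 is right for 50 evaluable patients.

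**Step 2: apply the same rule to fewer evaluable patients.** For each n, the critical count c is the smallest with P(X ≥ c | n, 0.24) < 0.05, and power is P(X ≥ c | n, 0.44).

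| Evaluable n | Critical count | Power |
|---|---|---|
| 50 | 18 | 0.901 |
| 49 | 18 | 0.879 |
| 48 | 18 | 0.854 |
| 47 | 17 | 0.891 |
| 46 | 17 | 0.867 |
| 45 | 17 | 0.839 |
| 44 | 16 | 0.880 |
| 43 | 16 | 0.853 |
| 42 | 16 | 0.823 |
| 41 | 15 | 0.868 |
| 40 | 15 | 0.838 |

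Power does not fall smoothly because the test is discrete, but no n from 40 to 49 reaches 0.90. The exact type I error for n = 40 to 50 lies between 0.0255 and 0.0487, so it always stays below 0.05.

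**Step 3: average over the number evaluable when 50 are enrolled.** Expected power = Σ over m of P(M = m) × power(m), with M ~ Binomial(50, 1 − r). The chance that all 50 are evaluable is (1 − r)^50.

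| Assumed loss r | Expected power | Risk of missing the goal | All 50 evaluable |
|---|---|---|---|
| 2% | 0.883 | 11.7% | 36% |
| 5% | 0.872 | 12.8% | 8% |
| 10% | 0.861 | 13.9% | 0.5% |
| 15% | 0.846 | 15.4% | below 0.1% |
| 20% | 0.824 | 17.6% | below 0.1% |

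**Step 4: enrolment that would restore an average power of 0.90.** The same formula with a larger enrolment N gives 0.902 for N = 54 at 5% loss (N = 53 gives 0.897), and 0.900 for N = 57 at 10% loss (N = 56 gives 0.895).

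**The case against.** The power sentence is explicitly conditional on evaluable patients, and on that condition it is accurate. Both places in the statistical section that give the 18/50 bar use the word evaluable, so one could read 50 as the evaluable target, with only an enrolment figure missing. Other text works to limit losses: patients are telephoned before each follow-up (Section 9.5), site staff review the requirements with them (Section 9.4), willingness to undergo the assessments is an entry criterion (Section 7.1), and Section 13.3 has all enrolled patients followed unless they withdraw consent. The effect is also modest. Power stays at or above 0.80 for every evaluable number from 39 to 50, which is up to 22% loss (11/50), and at 2% to 5% loss the drop is only 2 to 3 points.

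Much of this stands. The arithmetic is correct, the effect is moderate, and its size depends on an assumed loss rate. None of it removes the gap. If 50 means evaluable, enrolment must exceed 50 or lost patients must be replaced, and the plan provides for neither. The compliance measures may reduce losses, but they are not an allowance for them. Section 13.3 also conflicts with the termination rule in Section 9.3, and the two must be reconciled. However that is done, a patient who never receives TIF is outside the effectiveness population.

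**Conclusion.** The concern holds and should be fixed. With 50 enrolled, 0.90 is the ceiling on power. That direction needs no particular loss rate: every evaluable number from 40 to 49 falls short, by 1 to 8 percentage points. With losses of 5% to 20%, the risk of failing at a true rate of 44% is about 13% to 18%, rather than 10%. These averages rest on assumed loss rates and on loss being unrelated to the pH outcome. The decision rule is not at issue, because exact p < 0.05 against 24% applies at any denominator.

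**What to change.** State that 50 is the number enrolled and restate the power. Suggested wording: *50 patients will be enrolled. Power is 0.90 only if all 50 are evaluable at 6 months; if an assumed 10–20% are not evaluable (40–45 patients), exact power is 0.82–0.88.* The 10–20% is a placeholder, to be replaced by a rate the sponsor can justify. It would also help to note that 18/50 is the n = 50 case of the existing p < 0.05 rule and to list some other critical counts, such as 17/45, 16/42 and 15/40.

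This changes only the wording of the sample-size section. It adds no patients and leaves the analysis alone; the stated power becomes slightly less favourable.

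If 50 is meant as the evaluable number, the plan should say so and add either a replacement rule or a larger enrolment. Only this reading costs patients: 4 more (54 enrolled) at an assumed 5% loss, or 7 more (57 enrolled) at 10%, for an average power of 0.90.

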13.1. Causality and Seriousness Assessment

The Investigator and Sponsor will bring all expertise to bear on determining adverse event relationship to investigational device or other study treatment. The Investigator and Sponsor will promptly review documented adverse events and abnormal test findings to determine if the:

- Abnormal test finding or experience should be classified as an adverse event
- Adverse event was definitely, probably, possibly, unlikely or not related to the, and
- Adverse event meets the criteria for a serious adverse event.

Causality/Relationship Definitions:

Definitely	Clear-cut temporal association and no other possible cause.
Probably	Clear-cut temporal association and a potential alternative etiology is not apparent.
Possibly	Less clear temporal association; other etiologies are also possible, but there is a reasonable possibility that the incident, experience, or outcome may have been caused by the drugs, devices or procedures involved in the research
Unlikely	Does not follow a reasonable temporal association; or causal relationship with the drugs, devices or procedures involved in the research is unlikely but cannot be completely ruled out
Not related	AE is completely independent of study product administration; and/or evidence exists that the event is definitely related to another etiology.

13.2. *Reporting Serious Adverse Events*

Study personnel must report to the **EndoGastric Solutions Clinical Affairs Team** any SAE by telephone, fax, or electronic data capture entry within **24 hours** of learning of the event. When telephoning in notification of an event, a telephone log or other source record should be retained at site as adequate documentation of timely event reporting. When faxing in notification of an event, a fax confirmation report must be retained at site as adequate documentation of timely event reporting.

Attention: [name], FACS
Telephone Reporting: [contact]
E-mail Reporting:
[contact]

Study personnel must forward follow-up information as the event continues and/or resolves.

It is the responsibility of the Site Principal Investigator to inform the IRB of SAE and events as required by local procedure. EndoGastric Solutions is responsible for relaying adequate information on SAEs/UADEs to all participating investigators and regulatory authorities.

13.3. *Withdrawal of Subjects Due to Adverse Events*

Patients who experience adverse events during or after the procedure will remain enrolled in the study. Once enrolled, all patients will be followed for safety and efficacy evaluations with the exception of consent withdrawals by patient.

13.4. *Device Failures and Malfunctions*

All failures and malfunctions of the study device will be documented in the electronic database, and the device will be returned to EndoGastric Solutions for analysis. Device failures and malfunctions should also be documented in the patient's medical record.

NOTE: Device failures or malfunctions are NOT to be reported as adverse events. However, if there is an adverse event that results from a device failure or malfunction, that specific event would be recorded in the usual way.

14. Data Management

14.1. *Data Collection*

Data will be collected via a standard paper-based system of CRFs. In addition to collecting data as required per this protocol, various cost and reimbursement information will be captured on a per-patient and per-site basis. All data will be treated confidentially and exported only in the aggregate non-identifiable form.

14.2. *Data Processing*

Data will be entered into a spreadsheet based database by the CRO. Visual and computer error checks will be carried out. The Investigator will be queried on errors concerning completeness and consistency.

Audits may be performed for quality assurance of the electronic database.

15. Monitoring Procedures

15.1. *Monitoring and Auditing*

Monitoring visits to the clinical sites will be made periodically during the study, to ensure that all aspects of the current, approved protocol/amendment(s) are followed. Original source documents will be reviewed for verification of data.. The Investigator/institution guarantees direct access to original source documents by EndoGastric Solutions personnel, their designees, and appropriate regulatory authorities. In the event that the original medical records cannot be obtained for a patient that is seen by a non-study physician at a non-study institution, photocopies of the original source documents must be made available for review.

The study may also be subject to a quality assurance audit by EndoGastric Solutions or its designees, as well as inspection by appropriate regulatory authorities.

It is important that the Investigator and relevant study personnel are available during the monitoring visits and possible audits and that sufficient time is devoted to the process.

15.2. *Device Accountability*

Device accountability records must be maintained at the study site. Each site will purchase the devices from EGS.

16. Ethical Considerations

16.1. *Declaration of Helsinki*

The Investigator will ensure that this study is conducted in full conformity with the current revision of the Declaration of Helsinki, and with the regulations and guidelines of FDA; whichever affords the greater protection to the patient.

16.2. *Institutional Review Board*

A copy of the protocol, proposed Informed Consent form, other written patient information and any proposed advertising material must be submitted to the IRB for written approval. A copy of the written IRB approval of the protocol and Informed Consent form must be received by EndoGastric Solutions before recruitment of patients into the study.

The Investigator must submit and, where necessary, obtain approval from the IRB for all subsequent protocol amendments and changes to the Informed Consent form. The Investigator should notify the IRB of deviations from the protocol or SAEs/UADEs occurring at the site and other SAE/UADE reports received from EndoGastric Solutions in accordance with local procedures.

The Investigator will be responsible for obtaining annual IRB approval and renewal throughout the duration of the study. Copies of the Investigator's reports and the IRB continuance of approval must be sent to EndoGastric Solutions.

16.3. *Informed Consent Form*

A sample Informed Consent form is provided in Appendix A for the Investigator to prepare for use at his/her site. The written Informed Consent documents should be prepared in the language(s) of the potential patient population.

The reviewing IRB and the sponsor must first approve the Informed Consent forms that are used. The Informed Consent forms that are used should be in accordance with the current guidelines as outlined by the Good Clinical Practices (GCP) guidelines, Declaration of Helsinki and the International Conference on Harmonization (ICH).

Prior to participation in the clinical trial, each patient must give written Informed Consent after the context of the study has been fully explained to the patient in language that is easily understood by the patient. The patients must also be given the opportunity to ask questions and have those questions answered to their satisfaction.

Written Informed Consent must be recorded appropriately by means of the patient's, or their legal representative's dated signature. The patient will receive a copy of the Informed Consent form.

16.4. *Amending the Protocol*

This protocol is to be followed exactly, and will only be altered by written amendments. Administrative changes that do not affect the patient benefit/risk ratio (e.g., editorial changes for clarity) may be made without any further approvals. Any change that would require alteration of the Informed Consent form must receive approval from appropriate EndoGastric Solutions personnel and from the IRB prior to implementation. Following approval, the protocol amendment(s) will be distributed to all protocol recipients with instructions to append them to the protocol.

16.5. *Emergency Actions*

EndoGastric Solutions accepts the right of the Investigator to deviate from the protocol in an emergency when necessary to safeguard the life or the physical well being of a study patient. The Investigator must give notice of any emergency deviations and justification for the deviation to EndoGastric Solutions and the IRB as quickly as possible after the episode, in any event no later than 24 hours after the emergency.

16.6. *Protocol Deviations*

Deviations from clinical protocol requirements, including ICH/GCP guidelines, will be reviewed and evaluated on an ongoing basis and, as necessary, appropriate corrective actions put into place.

17. Study Administration

EndoGastric Solutions will make necessary efforts to ensure that this study is conducted in compliance with GCPs and all applicable regulatory requirements.

17.1. *Pre-Study Documentation Requirements*

Prior to shipment of investigational product, the following documents must be provided to CRO / EGS:

- Signed and dated Investigator Agreement
- A copy of the written IRB approval of the protocol
- A copy of the written IRB approval of the Informed Consent Form
- A copy of the curriculum vitae of the Coordinating Investigator and Co-Coordinator Investigator (if applicable)

17.2. *Record Retention*

The Investigator will maintain all essential trial documents and source documentation, in original format, that support the data collected on the study patients in compliance with the ICH/GCP guidelines. Documents must be retained for at least 2 years after the

last approval of marketing application or until at least 2 years have elapsed after last enrolled patient. These documents will be retained for a longer period of time by agreement with EndoGastric Solutions or in compliance with other regulatory requirements. When these documents no longer need to be maintained, it is EndoGastric Solutions responsibility to inform the Investigator. The Investigator will take measures to ensure that these essential documents are not accidentally damaged or destroyed. If for any reason the Investigator withdraws responsibility for maintaining these essential documents, custody must be transferred to an individual who will assume responsibility. EndoGastric Solutions must receive written notification of this custodial change.

17.3. *Criteria for Terminating Study*

EndoGastric Solutions reserves the right to terminate the study but intends only to exercise this right for valid scientific or administrative reasons and reasons related to protection of patients. Investigators and associated IRB will be notified in writing in the event of termination.

Possible reasons for study termination include (but are not limited to):

- The discovery of an unexpected, significant, or unacceptable risk to the patients enrolled in the study.

17.4. *Criteria for Suspending/Terminating a Study Center*

EndoGastric Solutions reserves the right to stop enrolling of patients at a study center at any time after the study initiation visit if no patients have been enrolled or if the center has multiple or severe protocol violations without justification or fails to follow remedial actions.

Possible reasons for suspending/terminating a study center include:

- Repeated failure to complete case report forms prior to scheduled monitoring visits.
- Failure to obtain written Informed Consent.
- Failure to report SAE/UADE to EndoGastric Solutions within 24 hours of knowledge.

17.5. *Investigator Responsibilities*

- Agree to sign and adhere to the Investigator Agreement
- Agree to participate in Investigator meetings as scheduled by EndoGastric Solutions
- Be willing to perform and be capable of performing treatment procedures as outlined in this protocol
- Comply with all required elements of this protocol Agree to obtain written Informed Consent before any study specific procedures are performed in accordance with GCP
- Complete all data modules prior to scheduled monitoring visits

